1 DEFINITIONS AND ABBREVIATIONS

Term	Description
ADE	Adverse Device Effect
AE	Adverse Event
AESI	Adverse Event of Special Interest
APHAB	Abbreviated Profile of Hearing Aid Benefit
AuSTIN	Australian Sentence Test in Noise
CBAS	Cochlear Bone Anchored Solutions AB
CDI	Cochlear Device Image
CHL	Conductive Hearing Loss
CIP	Clinical Investigation Plan
CMR	Controlled Market Release
CRF	Case Report Form
CRO	Contract Research Organisation
CSRI	Client Service Report Inventory
DD	Device Deficiency
EC	Ethics Committee Synonymous abbreviations/terms include: IEC (Institutional Ethics Committee or Independent Ethics Committee) HREC (Human Research Ethics Committee)
eCRF	Electronic Case Report Form
EDC	Electronic Data Capture
FDA	Food and Drug Administration
FS	Fitting Software
HARL	Hearing Aid Research Lab
HRQoL	Health Related Quality of Life
HUI	Health Utilities Index
GCP	Good Clinical Practice
ICF	Informed Consent Form
IFU	Instruction For Use
IMDRF	International Medical Device Regulators Forum
ISO	International Organization for Standardization
MHL	Mixed Hearing Loss
OFS	Osia Fitting Software
OTE	Off-The-Ear (sound processor)
PI	Principal Investigator

Term	Description
PSSRU	Personal Social Service Research Unite
PTA	Pure Tone Average
SADE	Serious Adverse Device Effect
SAE	Serious Adverse Event
SAP	Statistical Analysis Plan
SD	Standard Deviation
SNHL	Sensorineural hearing loss
SNR	Signal to Noise Ratio
SP	Sound Processor
SPL	Sound Pressure Level
SSD	Single-sided Sensorineural Deafness
SSQ	Speech, Spatial and Qualities of Hearing Scale
UADE	Unanticipated Adverse Device Effect
USADE	Unanticipated Serious Adverse Device Effect

2 CLINICAL INVESTIGATION SYNOPSIS

Investigation title	A multicentre, open, long-term clinical investigation evaluating safety, performance and Patient Reported Outcomes with an Active Osseointegrated Steady-State Implant System in adult subjects with conductive hearing loss, mixed hearing loss or single-sided sensorineural deafness.
Short title	LoTeOS
Investigation number	CBAS5793
Name of investigational medical device(s)	Active Osseointegrated Steady-State Implant System (OSI)
Intended use of investigational medical device(s)	
The Cochlear Osia 2 System uses bone conduction to transmit sounds to the cochlea (inner ear) with the purpose of enhancing hearing.
 
The Osia System is intended for adults and children (no minimum age limit) with conductive or mixed hearing loss (up to 55 dB HL) and single-sided sensorineural deafness (SSD), with a body weight of 7 kg* or more and sufficient bone quality and quantity to support successful implant placement.
 
*due to the potential presence of residual ethylene oxide after sterilisation of the device.

Name and description of comparator device/product(s)	Not applicable
Expected start date (first subject consented)	Feb-2021
Expected recruitment period	4 months
Expected duration per subject	12 months
Expected total duration of the clinical investigation	17 months
Number of subjects planned	Maximum 27
Number of investigational sites planned	3
Inclusion criteria	
 1. Subject has performed Hearing assessment at 3 and/or 6 months in the clinical investigation CBAS5751 2. Willing and able to provide written informed consent
Exclusion criteria	
 1. Unable to follow investigational procedures, e.g. to complete quality of life scales, or unwilling to comply with the requirements of the clinical investigation as determined by the investigator 2. Use of ototoxic drugs that could be harmful to the hearing, as judged by the investigator

Objectives and Endpoints	
Safety Objectives	Endpoints
Collect long term safety data	
 • Number and type of reported Adverse events (including explantations, revision surgery) • Number and type of reported Device deficiencies • Use of concomitant medication • Socio-economic data and health care utilisation related to hearing rehabilitation
Compare baseline audiogram before implantation with audiogram at follow up visits to investigate if the thresholds have been constant over time	
At 12 and 24 months:
 
 • Bone and air conduction thresholds, masked and unmasked
Performance Objectives	Endpoints
Collect and evaluate long term data on Device and Hearing Performance and compare it with the last performed measurement (3 or 6 months) in the clinical investigation CBAS5751	
At 12 and 24 months compared to last performed measurement (3 or 6 months) in CBAS5751:
 
 • Thresholds audiometry, sound-field [PTA4, Mean of 0.5, 1, 2 and 4 kHz] • Thresholds audiometry, sound-field [0.25, 0.5, 0.75, 1.0, 1.5, 2.0, 3.0, 4.0, 6.0 and 8.0 kHz] • Adaptive speech in noise [signal-to-noise ratio, 50% speech understanding] • BC-direct
Patient Reported Outcomes Objectives	Endpoints
Collect and evaluate long term data on Patient Reported Outcomes and compare it with the last performed assessment (3 or 6 months) in the clinical investigation CBAS5751	
At 12 and 24 months:
 
 • Self-reported assessments of hearing outcome: 
 ➢ Abbreviated Profile of Hearing Aid Benefit (APHAB) ➢ Speech, Spatial and Qualities of Hearing Scale (SSQ) • Health-related quality of life (HRQoL) 
 ➢ Health Utilities Index (HUI)
Collect Subjective experience of the investigational device and sound experience	
At 12 and 24 months self-reported assessment of:
 
 • Satisfaction with the investigational device • Experienced sound quality of the investigational device
Collect long term usability data and compare it with the last performed assessment (3 or 6 months) in the clinical investigation CBAS5751	
At 12 and 24 months:
 
 • Daily use • Daily streaming time • Battery lifetime • Magnet choice / Magnet change(s) required

	
(and why?)
 
 • Use of SoftWear pad • Sound Processor retention • Sound Processor wearing comfort
Exploratory Objective	Endpoint
Collect high frequency thresholds with the device using the CDI tool	
At 12 and 24 months:
 
 • Thresholds audiometry [at 6.0, 7.0, 8.0, 9.0 and 9.5 kHz]

3 SCHEDULE OF EVENTS

Visit Type	Screening/Visit 1	EOS
Timing of Investigation	12M post-surgery	24M post-surgery
Visit window (±)	± 22 weeks	± 4 weeks
Procedures		
Written informed consent	X	
Demographics (transfer from CBAS5751)		
Eligibility	X	
Audiogram	X	X
Sound processor fitting:		
• Coil to coil measurement	X	X
• BC direct	X	X
• Fine tuning	X ^a	X ^a
Blocking verification	X	X
Free field thresholds	X	X
Speech recognition in noise	X	X
High frequency thresholds	X	X
APHAB	X	X
SSQ	X	X
HUI	X	X
Satisfaction with the device	X	X
CSRI ^b	X	X
Usability:		
Daily use	X	X
Daily streaming time	X	X
Battery lifetime	X	X
Magnet choice	X	X
Use of Soft Wear pad	X	X
Retention	X	X
Comfort	X	X
Concomitant Medications ^c	X ^d	X
Adverse Events	X ^d	X
Device Deficiencies	X ^d	X
Device exposure	X	X
Extra visits as needed		

Abbreviations: APHAB, Abbreviated Profile of Hearing Aid Benefit; SSQ, Speech, Spatial and Qualities of Hearing Scale; HUI, Health Utilities Index;

CSRI, Client Service Receipt Inventory

^a Should be performed if needed.

^b Investigates economic consequences of hearing rehabilitation by capturing major health care costs and productivity losses.

^c Specify what types of concomitant therapies are applicable e.g. prescription medications, over-the-counter medications, vitamins, and herbal supplements, and non-pharmacologic therapies such as [insert any other relevant therapies such as acupuncture, electrical stimulation, special diets and exercise regimens].

^d From the 6-months visit in the CBAS5751 clinical investigation up to the 12-months visit.

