7 DESIGN OF THE CLINICAL INVESTIGATION

7.1 General

This is a multicentre, open, long term clinical investigation evaluating safety, performance and Patient Reported Outcomes (PRO) with the Osia 2 System in adult subjects 18 years or older with conductive hearing loss, mixed hearing loss or single-sided sensorineural deafness.

The subjects are the participants who performed the 3- and/or 6-month visit in the completed CBAS5751 investigation. The maximum number of subjects will be 27 from three clinics. The subjects will be followed at two visits, 12 and 24 months after the surgery date in the CBAS5751 investigation. The visit window at the 12-month visit will be opened as much as ± 5 months. The reason for this is to enable for as many subjects as possible to be included. At the time of investigation start the seven first implanted subjects in the CBAS5751 investigation have already passed their 12-month timepoint by several months. The performance of the device is not expected to change over this time period, but if it does, it will still be captured. This approach also provides the opportunity to collect safety data from the first seven subjects. At the final and most important time point 24 months, the visit window will be narrowed to ± 4 weeks.

The subjects will attend two scheduled investigation visits over a 12-month investigation period to be assessed as described in the Schedule of Events (Section 3). At investigation visits, subjects will be evaluated through objective audiological hearing tests, patient reported outcomes, questionnaires and safety assessments. The overall outcomes are to determine the hearing performance of the Investigational device at 12 and 24 months post-surgery and compare it with the last performed measurement (3 or 6 months) in the clinical investigation CBAS5751, assessed by sound-field thresholds audiometry, [PTA4, Mean of 0.5, 1, 2 and 4 kHz] and individual frequencies [0.25, 0.5, 0.75, 1.0, 1.5, 2.0, 3.0, 4.0, 6.0 and 8.0 kHz] and Adaptive speech recognition in noise. The self-reported outcomes will also be followed-up and compared with previous reported values. Safety will be assessed by recording and summarising all AEs/ADEs and DDs. A compilation of all AEs and DDs will be performed after all subjects have completed their 12-months visit. A full clinical investigation report will be prepared after the 24-month statistical analysis has been performed.

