7.1.1 Design Rationale

The rationale for the design of this investigation is the intention to collect long-term safety and performance Osia 2 system data to meet expected requirements from any Notified Body or Regulatory agency. Following subjects from the previous CBAS5751 clinical investigation is judged

as a fast and efficient way to collect such data, since these subjects are already implanted with the Osia 2 system. To be able to compare performance and safety of the device over time similar endpoints as in the previous investigation will be chosen. In addition, the subjects will be asked questions regarding device satisfaction, sound satisfaction, usability and health care utilisation to collect information for current and future comparison with other studies.

The audiometric thresholds (pure tone average PTA4 and individual frequencies) and speech recognition in noise measured in sound-field, are relevant and objective methods that are commonly used by clinics internationally as a way to assess hearing performance, and they were both used in the CBAS5751 investigation.

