7.4 Safety Evaluations and Procedures

Subjects will be carefully monitored during the investigation for possible adverse events and appropriate treatment of the subject will be initiated. Any adverse events observed will be fully investigated by the investigator and documented in the CRF including assessment of seriousness, severity (mild, moderate or severe) and relationship to the medical device. The risks and anticipated ADEs for Osia 2 System, as identified in Section 8.2 of the CIP, will be assessed in the clinical investigation via reporting of all AEs/ADEs from the time of first subject first visit until last subject last visit. The Sponsor will be notified by automatic eCRF alerts when events are judged as device related or serious. A safety monitor, appointed by the Sponsor, will be contacted regarding events that are uncertain, serious or unexpected.

When all 12 months visits have been performed an interim safety evaluation will be performed

regarding all AEs and DDs reported. This evaluation will be performed by the team responsible for the clinical investigation, including the Safety contact/monitor. The interim safety evaluation will be documented in a report.

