9.10 Interim Analyses

An interim safety analysis will be performed when all subjects have completed their 12-months visit. A compilation of all AEs and DDs that occurred between the 6-months visit in CBAS5751 and the 12-months visit in this investigation will be performed. In addition, follow-up of any unresolved AEs at the 6-month visit in CBAS5751 will be done.

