11.2 Recording and Handling of Adverse Events

Subjects shall be carefully monitored during the clinical investigation and the investigator should enquire about AEs at each visit.

All AEs will be recorded from the last visit in the CBAS5751 investigation. AE recording will continue for each subject until completion of the final visit. Ongoing SAEs, SADEs and/or AESI will be followed for 30 days, or until resolution or stabilisation of the event, whichever comes first.

Source notes should indicate the evaluation for AEs, even if none to report. All required AEs will be reported if observed, even if anticipated and/or acknowledged as a risk factor in the consent.

All AEs will have the following information documented: start and stop dates, action taken, outcome, severity and investigators opinion on the potential relationship to the Investigational device and investigational procedures. If an AE changes in severity, the most severe (highest) grade will be captured for that event on the Adverse Events CRF.

Adverse events will be summarized by either IMDRF or CTCAE to System Organ Class (SOC) and IMDRF/CTCAE term. Decision will be taken in due time before database lock.

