11.3 Recording and Handling of Device Deficiencies

Subjects shall be carefully monitored during the clinical investigation and routinely questioned about DDs at investigation visits. Source notes should indicate the evaluation for DDs, even if none to report.

The Investigator shall assess if the DD led to an AE or could have led to a serious medical occurrence (serious adverse device effect) if;

- a) suitable action had not been taken,
- b) intervention had not been made, or,

c) circumstances had been less fortunate

All DDs will be documented in the source notes and the DD page of the CRF.

All explanted implants shall be sent to Device Analysis according to company procedures. Implants and Sound Processors should be sent to CLTD.

In case of any DD and/or explantation of an implant, site should contact the sponsor, whom will then provide the site with a RETRIEVED DEVICE KIT for return of the implant and further instructions on the return process. In case of any DD of a Sound Processor the site should contact the sponsor for further return details.

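### AEs and device deficiencies between CBAS5751 and Visit 1 are gathered retrospectively by questioning and pooled with later follow-up, so event rates may be biased downward by an unknown amount

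*Combined protocol and SAP*

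**What the plan says.** Section 7.1 sets the contact schedule: "The subjects will attend two scheduled investigation visits over a 12-month investigation period". The Schedule of Events (Section 3) puts written consent at Visit 1, at month 12 ± 22 weeks after surgery, and the final visit at month 24 ± 4 weeks. Its footnote d gives the AE, DD and concomitant-medication period for Visit 1 as "From the 6-months visit in the CBAS5751 clinical investigation up to the 12-months visit".

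On how events are found, Section 11.2 says "the investigator should enquire about AEs at each visit", and Section 11.3 says subjects are "routinely questioned about DDs at investigation visits".

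The interim safety analysis in Section 9.10 is "A compilation of all AEs and DDs that occurred between the 6-months visit in CBAS5751 and the 12-months visit in this investigation", plus follow-up of AEs still unresolved at the CBAS5751 6-month visit. For the final analysis, Section 9.1 presents AEs and DDs as numbers of events and of subjects with events, without division by visit. Section 7.1.1 explains the choice of endpoints similar to those of CBAS5751: "To be able to compare performance and safety of the device over time".

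The start of AE collection is stated in three ways. Section 3 (footnote d) and Section 9.10 use the CBAS5751 6-month visit. Section 11.2 says "All AEs will be recorded from the last visit in the CBAS5751 investigation", which is month 3 for anyone who did not attend month 6. Section 7.4 refers to "reporting of all AEs/ADEs from the time of first subject first visit until last subject last visit".

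**The concern.** Everything that happened to a subject between leaving CBAS5751 and attending Visit 1 pre-dates consent to this study. No diary, telephone contact or mandatory record review covers that gap, so the new events in the interim compilation are collected retrospectively. The gap is long for some identifiable subjects: Section 7.1 says the first seven implanted had already passed month 12 by several months when the study started.

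Minor events are the ones most exposed. In CBAS5751, 51 of 54 AEs were mild, and 70 of 89 DDs concerned the sound processor (Section 4.2.2.1.2). If part of these is missed, the rate after month 6 will look lower than it was. Because the final tables pool the retrospective period with later follow-up, a reader could not see which part of the count is affected. At stake is how far this study's AE and DD data can be set beside those of CBAS5751 in a report intended for regulators (Section 4.1).

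**Working it through.** **Plan figures reproduced.** From Section 4.2.2.1.2: 22/29 = 75.9% of subjects with an AE; related AEs 5 + 12 + 10 = 27; DDs 70 + 11 + 7 + 1 = 89. All agree. The plan gives no expected event count for this study.

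**Length of the look-back.** Inputs: Visit 1 window ± 22 weeks (Section 3) and a CBAS5751 visit held at month 6.
- 22 weeks is 5.06 months, so Visit 1 falls at month 6.94 to 17.06.
- Look-back: 6.94 − 6 = 0.94 to 17.06 − 6 = 11.06 months; nominally 6.
- Share of months 6 to 24: 0.94/18 = 5%, 6/18 = 33%, 11.06/18 = 61%. The extremes are window limits, not expected values.
- For a subject last seen at month 3, the Section 11.2 start point adds 3 months. Under footnote d, months 3 to 6 are not covered for that subject.

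**CBAS5751 rates.** Events/(29 × 6 subject-months): AEs 54/174 = 0.310 and DDs 89/174 = 0.511 per subject-month. This treats all 29 subjects as followed for 6 months.

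**Expected counts if the rate stayed constant.** 27 subjects × months × rate × capture, where capture is the fraction of events recorded relative to CBAS5751. The documents give no capture fraction, so the values below are assumptions.

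| Capture (assumed) | AEs, 6 months | DDs, 6 months | AEs, 18 months | DDs, 18 months |
|---|---|---|---|---|
| 1.0 | 50.3 | 82.9 | 150.8 | 248.6 |
| 0.8 | 40.2 | 66.3 | 120.7 | 198.9 |
| 0.5 | 25.1 | 41.4 | 75.4 | 124.3 |

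CBAS5751 itself had 54 AEs and 89 DDs.

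- The rate per subject-month falls in proportion to capture: capture of 0.8 gives a rate ratio of 0.8.
- The month 6 to 24 total falls below CBAS5751 only if capture is under 174/(27 × 18) = 174/486 = 35.8%, for AEs and DDs alike.
- Over a nominal 6-month interim period, the count is below CBAS5751 even at full capture (50.3 against 54; 82.9 against 89), simply because there are 27 subjects and not 29.

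**Can a true fall be told from under-capture?** In CBAS5751, 12 + 10 = 22 of 54 AEs were related to the procedure, alone or jointly with the device.
- If none of these recurred after month 6 and capture were complete: (54 − 22)/174 = 0.184 per subject-month, and 27 × 6 × 0.184 = 29.8 AEs.
- If the rate were unchanged and capture were 0.6: 50.3 × 0.6 = 30.2 AEs.

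The two explanations predict practically the same interim count.

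**The case against.** Retrospective is not the same as recalled. Clinic notes are a named source (Section 14). Sites contact the sponsor about DDs and device returns (Section 11.3), and supply and return of replacement processors are tracked (Section 12). SAEs, AESIs and DDs that could have led to a SADE are reported within 24 hours of awareness (Section 11.4.1), and extra visits are allowed. The CSRI asks separately about healthcare use over the previous 12 months. AEs carry start and stop dates, so they could be split by period afterwards, and the interim report already shows the earlier period alone. No AE or DD comparison with CBAS5751 is specified: Section 9.6 only tabulates, and Section 9.3 rules out hypothesis testing. The one safety pass/fail rule concerns related serious events with a shared root cause, which are unlikely to be forgotten.

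Most of this stands as a limit on the size of the problem. It does not close the gap. The 24-hour route depends on the site becoming aware, this study's device procedures operate mainly after Visit 1, the CSRI is itself self-reported, and nothing requires any of these records to be checked against the AE and DD forms for the period before consent.

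A reader might go further and infer that all interim safety data are recalled and that counts must drop below those of CBAS5751. The documents do not support either step. Hospitalisations, revisions and replacements normally leave records, and the interim analysis also follows AEs already recorded as unresolved. Longer follow-up raises total counts unless capture is below about 36%. Nor do the documents say how completely CBAS5751 captured events, or that its processor deficiencies were brief.

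**Conclusion.** The point holds as a risk of downward bias of unknown size in the observed rate of minor AEs and DDs per subject-month. It applies most clearly to the period before Visit 1 (nominally 6 months, about 0.9 to 11.1 with the window) and, less strongly, to the nominal 12 months before the next scheduled questioning. It is neither a prediction that totals will fall nor evidence that events have been missed. The related-SAE pass/fail rule is the least affected.

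The arithmetic assumes 27 subjects with complete follow-up, 29 × 6 subject-months in CBAS5751, a CBAS5751 visit on time at month 6 and a constant event rate. The last is doubtful for AEs, since a true fall in procedure-related events after month 6 is likely. That makes separate reporting more useful, because pooled counts cannot distinguish such a fall from under-capture.

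**What to change.** 1. In Sections 11.2 and 11.3, require at Visit 1 and at the end-of-study visit a review of clinic notes and of the sponsor's service, replacement and return records for that subject, back to the last CBAS5751 visit. Mark each event's source as dated record or subject report.
2. In Sections 9.1, 9.6 and 9.10, tabulate the period from the last CBAS5751 visit to Visit 1, labelled retrospective, separately from Visit 1 to month 24. Add events per subject-month to the counts, and state the ascertainment caveat beside any comparison with CBAS5751. As Section 9.1 says no separate SAP is planned, this has to be written into the CIP.
3. Reconcile the AE start point among Section 3 (footnote d) and Section 9.10, Section 11.2, and Section 7.4, so that subjects last seen at month 3 have no uncovered interval.

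The cost is a short record check for at most 27 subjects, one eCRF field and one table split. Event counts may come out slightly higher.

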4 BACKGROUND INFORMATION AND RATIONALE

4.1 Introduction

The aim of this investigation is to collect long-term safety and performance data with the Active Osseointegrated Steady-State Implant System, Cochlear™ Osia® 2 System, by following subjects from the previous Osia clinical investigation CBAS5751. This is to meet expected requirements from any Notified Body or Regulatory agency. In addition, questions regarding device satisfaction, sound satisfaction, usability and health care utilisation will be asked. This data can be used for current and future comparison with other studies, and for supporting marketing claims.

